## **Research Summary**

NCT03370757

- 1. **Protocol Title** Very Low Birth Weight (VLBW) Preterm Infant Health Outcomes with Bundled Care in the Neonatal Intensive Care Unit: A RCT
- 2. Purpose of the Study Explore the impact of bundling nursing care activities on the overall health of VLBW preterm infants who receive bundled care in a Level IV Neonatal Intensive Care Unit (NICU). Specific study aims include:
  - **Aim 1.** Evaluate differences in infant health when diaper changes occur at 3- versus 6-hours during 3-hour bundled care.
    - **RQ1.** What caregiving activities other than diaper changes are included in *bundled care events* and do they differ when diaper changes are bundled every 3 versus 6 hours.
    - **RQ2.** Does infant physiological stability ( $\Delta$  heart rate,  $\Delta$  respiratory rate,  $\Delta$  oxygen saturation, # apnea # bradycardias, # desaturations, feeding tolerance) differ **between 3- and 6-hour bundled care diapering**?
    - **RQ3.** Does infant weight gain over time differ between 3- and 6-hour bundled care diapering?
    - **RQ4.** Within the 6-hour bundled diaper care group, does infant physiological stability ( $\Delta$  heart rate,  $\Delta$  respiratory rate,  $\Delta$  oxygen saturation) differ between bundled care with and without a diaper change (3 versus 6-hours)?
  - **Aim 2.** Evaluate differences in infant skin health between 3- and 6-hour bundled care diapering at two sites (buttocks and chest).
    - **RQ1.** Does skin transepidermal water loss (TEWL) differ over time and at the end of 6 weeks between 3- and 6-hour bundled care diapering on the chest and buttocks?
    - **RQ2.** Do neonatal skin condition scores differ over time and at the end of 6 weeks between 3- and 6-hour bundled care diapering?
    - **RQ3.** Does skin pH differ over time and at the end of 6 weeks between 3- and 6-hour bundled care diapering?
    - **RQ4.** Does the skin microbiota differ over time and at the end of 6 weeks between 3- and 6-hour bundled care diapering?
  - **Aim 3.** Evaluate the acceptability and feasibility of conducting a bundled care intervention where the frequency of one care activity, diaper care, is standardized.
    - **RQ1.** What are the perceptions of parents and providers about the criteria necessary for conducting a diaper change in the NICU?
    - **RQ2.** What are the perceived barriers of parents and providers to longer timeframes between diaper changes?

**Exploratory health outcomes** will examine the incidence of late onset sepsis and urinary tract infections in both bundled care groups.

#### 3. Background & Significance -

Progress in perinatal medicine has resulted in an increased survival rate of very preterm infants (typically ≤ 1500 grams and < 34 weeks). However, preterm infants' growth and developmental outcomes vary with illness severity and degree of neurological insult (Boyle et al., 2012; Ge et al., 2013) and unpredictable variations in outcomes exist even among healthy preterm infants (Schneider et al., 2014; Vohr, 2014). Preterm infants also have poorer

orientation, self-regulation, and reflexes and more excitability, hypotonia, and hypertonia at 40 weeks postmenstrual age (PMA) when compared to term infants (Pineda et al., 2013). The variations in preterm infants' outcomes have led to the supposition that the NICU environment may negatively impact the health and development of these infants and significant research has been devoted to examination of light, noise, and caregiving interventions (Boo et al., 2002; Brandon et al., 2017; Brandon et al., 2002; Morag & Ohlsson; 2013).

In addition, individualized developmental care has become the norm in most NICUs since developmental care was first promoted by [name] in the 1980s (1982). A body of literature has emerged to support the observation of infant behavioral organization (infant cues) in response to the stress of the NICU environment to guide caregiving to minimize infant stress and optimize infant outcomes. The overall goal of individualized developmental care is to promote the short- and long-term health and development of high risk infants including interventions that promote the well-being of an infant's family (Macho, 2017). Consequently, many NICUs have implemented neuroprotective strategies to reduce over simulation, promote sleep and facilitate brain development in all high-risk infants (Gressens et al., 2002; Lucas-Thompson et al., 2008).

One neuroprotective strategy includes the grouping of care activities around a single caregiving event described as "clustering" or "bundling care". Individualized developmental care dictates that a bundled care event is halted if an infant displays significant behavioral stress cues. Yet, the number and type of caregiving activities that are included in bundled care and the timeframe between bundled care events has not been systematically studied. While painful and intrusive interventions like heel sticks are often described as a source of infant stress (Lucas-Thompson et al., 2008) routine interventions like diaper changes can also be a high stress event (Mörelius et al., 2006). Current bundled care typically includes a diaper change, but the timeframes between bundled care events differ based upon infant illness severity. postmenstrual age, and individual NICU practice standards. Currently no operational definition exits around the expected length of time that categorizes a bundled care event from a nonbundled care event. In our pilot work of five extremely low birth weight (ELBW) infants we identified a caregiving event as including at least two nursing care activities and lasting at least five minutes. Over the first 14 days of life in the NICU, 161 bundled care events were identified, averaging 4.7 events per day per infant. The average duration for bundled care events greater than 5 minutes was 10.8 minutes. The time between bundled care events was 2.9 hours.

The inclusion and exclusion of certain care activities in any individual care event is often dictated by the infant's treatment plan or needs, but some activities like diapering may be optional. Understanding the impact of when to include optional, yet stress provoking interventions, will allow us to minimize overall environmental stress in hospitalized VLBW infants. It is unclear how the different times used in bundled care affect overall infant health including skin health in the diapered area. Therefore, given the lack of data around bundled care, we aim to explore the impact of bundling diaper care activities on overall health of VLBW preterm infants. We will include a focus on skin health because it is important to understand the benefits of decreased infant stress and any potential skin health trade-offs associated with longer versus shorter time between diapering care. Findings from this study will allow us to better understand the relationship between neonatal skin health while providing developmentally appropriate bundled care.

### 4. Design & Procedures

**a. Design and Setting.** A randomized controlled designed will be used to evaluate the effect of *bundled diaper care* on overall infant and skin health. Infants will be recruited from the Level IV Intensive Care Nursery (ICN) at Duke University Hospital. The ICN is a Level IV, 67-bed nursery and one of the area's leading referral centers for infants born prematurely. The

Duke ICN has an average daily census of 90% and annually admits 150 VLBW infants. The ICN practices individualized developmental care with standard bundled care intervals that vary based upon an infant's birth weight and feeding status (every 3, 4, or 6 hours). Infants who are admitted or transferred to one of the ICN three stepdown units will also be considered if eligible and will continue to receive the intervention when transferred including the Special Care Nursery at Durham Regional Hospital. The principal investigator has been a clinical nurse specialist affiliated with the ICN since 1993 and has the support of the nursery medical and nursing team to conduct this research including the Division of Neonatology, the ICN Intensive Care Developmental Care Team and the Medical Director.

**b. Participants.** A maximum of 80 VLBW infants will be recruited to ensure at least 25 infants in each study group with complete data. Ten parents of infant participants (5 in each study group) and 10 health care providers will participate in interviews about the acceptability and feasibility of the diapered bundled care intervention. The goal of this study is to enrich the literature with estimation of values and variances of the outcomes measured as well as how these values change over time. With a total sample size of 50 VLWB infants, we are confident that we will be able establish effect to inform a larger subsequent study. Because most of the infants are expected to receive care up to 6-weeks, we expect little missing data or participant attrition.

#### Infant Inclusion criteria are:

[figure not shown]
- 1. Must be participating in the ICN standard 3-hour bundled care
- 2. Must wear a breathable diaper
- 3. Must be  $\leq$  32 weeks gestation at birth
- 4. Infants are expected to remain hospitalized for at least 4 weeks

### Infant Exclusion criteria are:

- 1. Neonatal Abstinence Syndrome
- 2. Humidified incubator
- 3. Diaper rash
- 4. Pre-existing or genetic skin conditions
- 5. Severe illness requiring 1:1 nursing care: e.g. minimal stimulation protocol, high frequency ventilation, vasopressor drug support, or body cooling.

Infants will be recruited and enrolled as soon as they meet study criteria (**see Figure 1**. **Study Schemata**). Data collection will begin following study enrollment and will continue until 6 weeks following randomization (**see Table 1**).

Figure 1. Study Schemata

c. Intervention: Infants will be randomly assigned and stratified by birth weight (≤ 800 grams, >800 grams to 1150 grams, > 1150 grams) to either 3- or 6- hour bundled diaper care. All infants will receive bundled care per unit standards until they are eligible for 3-hour bundled care. Infants typically transition to 3-hour bundled care once they are receiving interval feedings every three hours. This transition usually occurs before 3 weeks chronological age in infants >800 grams at birth and by 6 weeks

for infants ≤ 800 grams. Other care activities included in the standard 3-hour bundle vary based upon infant treatment needs, but usually include a diaper change. The only difference in a 3-hour and 6-hour bundled care event will be the timing of the diaper change. Infants will receive a diaper change at either 3 or 6 hours. While 3-hour bundled care is standard of care, this is a clinical environment in which caregiving cannot be expected to occur exactly every three hours to the minute, therefore both expected and actual times for the bundled care events will be collected to include in data analysis as needed. Infants who are receiving the 6-hour bundled diaper care will continue to receive 3-hour care interventions for all other interventions or as dictated by infant care needs. At the 3-hour caregiving interval in which the 6-hour bundled care infants are not due for a diaper change, the nurse will peek into the diaper to ensure there are no stool present. If stool is present, a diaper change should occur and the deviation from the protocol noted in the bedside documentation.

d. Procedures: A neonatal provider will give approval for participation in the study. Parents will be approached for consent after eligibility screening is completed (≤ 32 weeks gestation). The principal investigator is a clinical nurse specialist and nurse scientist who has been affiliated in the Intensive Care Nursery since 1993. Study personnel will explain the study, allow time for questions, have a parent sign the consent form, and a copy will be given to the parent. Parents will provide consent for their infant's participation in the study and will give permission for themselves to participate in an interview about the study, if selected. Five parents from each group will purposively selected to participate in an interview. Parents will be selected to include parents with infants < 1000 grams at birth and parents with infant ≥ 1000 grams at birth.

[figure not shown]
Following consent, the infant will be monitored until all inclusion and exclusion criteria are met. At that time randomized to an intervention group and data collection will be initiated. The intervention will continue for six weeks at which time collection of data will stop and bundled diapered care will resume according to unit protocol. If the infant no longer meets inclusion criteria the intervention will be discontinued and routine data collection will be discontinued. The exclusion criteria will be noted, e.g. use of diaper cream, and data collection regarding any new illness characteristics or treatments will continue. If an infant requires a diaper change due to a stool or other needed procedure this will be recorded on a bedside card.

Ten nurses will be recruited for participation in interviews around intervention acceptability at the end of the study.

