### 10. Data Analysis and Statistical Considerations

Initially, we will conduct descriptive analyses, including examination of means and proportions and the measures of variability for each variable overall and by bundled care groups. The descriptive analyses will be followed by modeling approaches to respond to the research questions. Tests of statistical significance will be two-sided and the threshold for statistical significance will be P < 0.05.

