## Aim 2. Evaluate differences in infant skin health between 3- and 6-hour bundled care diapering at two sites (buttocks and chest)?

# **RQ1**. Does skin transepidermal water loss (TEWL) differ over time and at the end of 6 weeks between 3- and 6-hour bundled care diapering on the buttocks and chest?

**Analysis:** The trajectories of TEWL measured across the 18 days of bundle care will be fitted using a linear mixed model with a random intercept. We will first determine the best trajectory fit for TEWL over the 18 days. Once we select an appropriate trend for the data a model similar to the one described for weight will be estimated. We will remove technology burden scores and add time varying covariates for time since last bath, urine output, stool pattern, and feeding type indicator.

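### No pH or TEWL reading is fixed before the assigned diaper interval starts and no Aim 2 model uses a baseline value, so the week-6 skin comparison loses precision

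*Combined protocol and SAP*

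**What the plan says.** Section 4d (Procedures) follows the infant from consent until all criteria are met, and then: "At that time randomized to an intervention group and data collection will be initiated". The paragraph after the exclusion criteria in section 4 adds only this: "Data collection will begin following study enrollment". Table 1 ties pH, TEWL and the swab to the observations three times a week. The neonatal skin condition score (NSCS) is recorded twice a day by staff nurses. None of these entries names a baseline visit or relates the first reading to the first assigned diaper interval.

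For Aim 2 RQ1, section 10 says: "The trajectories of TEWL measured across the 18 days of bundle care will be fitted using a linear mixed model with a random intercept". The form is that of the weight model: arm (b1), day (b2), arm by day (b3) and postmenstrual age (PMA). Technology burden is dropped, and bathing, urine, stool and feeding covariates are added. The pH and NSCS models follow the apnea template with the same changes. In both templates the estimate of interest is b3. No Aim 2 model has an observed baseline skin value, although RQ1 to RQ3 ask about the arm difference at week 6 as well as over time.

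**The concern.** If the first skin reading is taken after the 6-hour interval has begun, it may already carry some effect of the intervention. The fitted start-of-study difference, b1, then mixes chance imbalance with any early effect, and nothing in the data separates the two. A rapid, sustained change in pH or TEWL would fall largely into b1, outside the estimate that the plan singles out.

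The week-6 contrast is b1 plus b3 times the length of follow-up. Because b1 is estimated freely, this contrast keeps the stable between-infant variation that a measured baseline could partly remove. With about 25 infants per arm, and a study meant to supply estimates and variances for a larger one, that precision is worth having. The common condition needed for a baseline already exists: infants must be on 3-hour bundled care, which usually includes a diaper change, before they are randomised.

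**Working it through.** **Inputs from the documents.** Section 4b plans to "ensure at least 25 infants in each study group with complete data", that is 2 × 25 = 50 infants. Three observations a week for 6 weeks give 3 × 6 = 18 values, the figure used in section 10. No power, effect size, standard deviation or correlation is stated, so the sample size has no derivation to reproduce.

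**Assumptions.** All 18 values are present and equally spaced (visits 0 to 17); total variance is 1; the random intercept has variance ICC and the residual 1 − ICC; change is linear; there are no other covariates. The baseline coefficient is treated as known, which is slightly optimistic. The ICC is not given and is varied from 0.1 to 0.7.

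**Week-6 contrast, planned form (b1 free).** Visits have mean 8.5 and sum of squares 484.5.

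Variance A = (2/25) × [ICC + (1 − ICC) × (1/18 + 8.5²/484.5)] = 0.08 × [ICC + 0.2047 × (1 − ICC)].

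**Week-6 contrast, first value as pre-intervention covariate.** Seventeen visits remain, with mean 9 and sum of squares 408. The intercept variance left after conditioning is ICC × (1 − ICC).

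Variance B = 0.08 × [ICC × (1 − ICC) + (1 − ICC) × (1/17 + 8²/408)] = 0.08 × (1 − ICC) × (ICC + 0.2157).

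| ICC | A / 0.08 | B / 0.08 | B / A |
|---|---|---|---|
| 0.1 | 0.284 | 0.284 | 1.00 |
| 0.3 | 0.443 | 0.361 | 0.81 |
| 0.5 | 0.602 | 0.358 | 0.59 |
| 0.7 | 0.761 | 0.275 | 0.36 |

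With random slopes added (slope variance 0.25 or 0.5 over the whole follow-up), generalised least squares gives B/A of 0.88 or 0.91 at ICC 0.3, 0.71 or 0.78 at 0.5, and 0.52 or 0.61 at 0.7. At ICC 0.1 it stays at 1.00.

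**Slope b3, first value as covariate.** The random intercept already removes stable differences between infants, so the only effect is the lost time point: 484.5/408 = 1.19. With random slopes the factor is 1.05 to 1.13. The covariate therefore makes b3 slightly less precise.

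**Slope b3, common baseline mean (b1 = 0).** The sum of squared visits is 1785 and the sum of visits is 153. The factor is 484.5 / [1785 − ICC × 153² / (1 − ICC + 18 × ICC)].

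- ICC 0.1: 484.5/918.0 = 0.53
- ICC 0.3: 484.5/633.7 = 0.76
- ICC 0.5: 484.5/553.0 = 0.88
- ICC 0.7: 484.5/514.7 = 0.94

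With random slopes the range is 0.68 to 0.98. This gain assumes that the arm difference grows linearly from zero at baseline.

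**The case against.** The plan already handles part of the problem. The TEWL model has a random intercept, which its template describes as the infant's own baseline. PMA is a covariate, and randomisation is stratified by birth weight. A stable imbalance at entry goes into b1, not into b3. A reader might infer that the arm contrast carries all the between-infant variation, or that imbalance can never be told from an effect; the documents support neither. What stands is narrower. The random intercept is a latent term, and in the template used for pH the need for one is only to be assessed. PMA and birth weight are proxies for skin state. The split between b1 and b3 does not help the week-6 contrast, or an effect that appears before the first reading.

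A reader might also apply the usual 1 − r² rule. At r of 0.3, 0.5 or 0.7 it gives 25/0.91 = 27.5, 25/0.75 = 33.3 or 25/0.51 = 49.0 equivalent infants per arm. That rule describes an unadjusted comparison of one week-6 value, which is not the planned analysis.

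Nor do the documents show that the first reading is taken after treatment has begun. They leave the order open, and the study schema is not visible in the extract and might mark a baseline.

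Finally, the swab needs a diaper free of stool and so cannot be guaranteed at a set visit. NSCS is not one of the 18 assessments, and with diaper rash excluded at entry it probably varies little at the start. Both points stand and limit the remedy.

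**Conclusion.** The point holds for TEWL and pH at week 6. No pre-intervention reading is fixed, and the models use no observed baseline, so the week-6 contrast is less precise than the schedule allows and b1 cannot be read cleanly. Randomisation still makes the arms comparable in expectation, so a reader should not infer bias.

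The possible saving in week-6 variance runs from nothing at ICC 0.1 to 64% at ICC 0.7. It is smaller if slopes vary between infants or if PMA already explains much of their difference. These figures are illustrations: they rest on assumed correlations and complete data, and for pH also on a normal model with a random intercept. For b3 a baseline covariate brings no gain; a common baseline mean does, if the linear form holds. For NSCS the gain is probably small.

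**What to change.** - **Timing.** State in section 4d and Table 1 that the first planned pH and TEWL reading, chest and buttocks, is taken at a routine diaper change at or just before randomisation and before the assigned interval starts. Take the swab then if no stool is present. For NSCS, use the last score before the assigned interval, if one was recorded.
- **Model.** Fit the TEWL and pH models with the arms constrained to a common mean at that reading, or use the reading as covariate for the week-6 contrast only. Fix the timing first: otherwise the model would condition on, or constrain, a value that may already reflect the intervention. If an abrupt early effect is plausible, allow a step after baseline; this gives up the gain for b3.
- **Reporting.** Report the week-6 contrast with its confidence interval beside b3, and report the baseline-to-follow-up correlation for the design of the larger study.

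The cost is one fewer post-intervention skin point and a short change to the model text. Because Table 1 ties skin readings to the observations, moving the whole observation would also take one day from Aim 1. Moving only the skin reading avoids that.

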- vii. Neonatal Skin Condition Score (see Figure 2): The NSCS will be collected twice daily (day and night shift by staff nurses) while infants are participating in the study. The NSCS is a reliable and valid measure of skin condition (Lund & Osborne, 2004)

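### Losing eligibility, including for skin reasons, ends routine data collection, so Aim 2 skin measurements can stop because of the skin condition under study

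*Combined protocol and SAP*

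**What the plan says.** The rule is in Section 4.d: "If the infant no longer meets inclusion criteria the intervention will be discontinued and routine data collection will be discontinued". The next sentence limits what goes on afterwards: "The exclusion criteria will be noted, e.g. use of diaper cream, and data collection regarding any new illness characteristics or treatments will continue".

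Other sections bear on the same question:

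- Section 4.b, after the exclusion list, gives a general period with no exception: "Data collection will begin following study enrollment and will continue until 6 weeks following randomization".
- Sections 4.b and 5 both list diaper rash as an exclusion criterion.
- Section 4.e.vii has the neonatal skin condition score (NSCS) "collected twice daily (day and night shift by staff nurses) while infants are participating in the study".
- Section 8 discontinues the intervention at NSCS 5 or more in the diapered area and follows the infant until the problem resolves. It names no study measurements.
- Section 4.b (Participants) recruits up to 80 infants "to ensure at least 25 infants in each study group with complete data" and states that "we expect little missing data or participant attrition". The reason given is the expected length of care.
- Section 10 plans a random-intercept mixed model for TEWL and repeated-measures generalized linear models for NSCS and pH. It names no analysis set and does not say how stopped infants are handled.

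**The concern.** Aim 2 asks whether skin outcomes differ between arms over time and at the end of 6 weeks. If worsening skin ends measurement, the infants who would show a skin cost of longer diaper intervals are the ones whose later readings are missing. With the same trigger in both arms, the arm with worse skin loses more of its worst trajectories, and a true difference tends to be understated.

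The stakes go beyond this trial, because the study is meant to "enrich the literature with estimation of values and variances of the outcomes measured" and to inform a larger one. A systematic error would carry into that planning. Later TEWL, pH and swab readings that were never taken cannot be recovered.

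**Working it through.** **1. Does the rule reach skin reasons?** Read literally, the Section 4.d rule refers to inclusion criteria, whereas diaper rash is an exclusion criterion. The sentence after it, however, speaks of exclusion criteria and gives a skin treatment as its example, so skin reasons are meant. Diaper cream itself is on neither exclusion list. What continues (new illness and treatments) does not cover TEWL, pH, NSCS or swabs.

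**2. Does another section restore measurement?** Section 4.b's 6-week statement is general and conflicts with the specific rule. Section 4.e.vii ties NSCS to participation, which is not defined for a stopped infant. Section 8 is silent on study measurements. Section 10 does not address it.

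**3. What a stop removes.** The plan's 18 observation days reproduce: 3 per week × 6 weeks = 18. Under Section 4.d, a stop at day 14 leaves 3 × 2 = 6 of 18 days, and 2 × 14 = 28 of 2 × 42 = 84 twice-daily scores. Section 10's statement that each infant has 18 days cannot hold for such an infant.

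**4. Is a stop rate implied?** No. Recruiting 80 for 2 × 25 = 50 complete allows 1 − 50/80 = 37.5% incomplete, while 5% or 10% attrition would need only 50/0.95 = 53 or 50/0.90 = 56 infants. Consent precedes randomization, so part of that margin may cover losses before randomization.

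**5. Size, same trigger in both arms (all inputs assumed).** 40 infants per arm, 18 equally spaced visits. Variances: intercept 0.4, slope 0.3, residual 0.3, so the week-6 SD is √(0.4 + 0.3 + 0.3) = 1. The true difference grows linearly to 0.50 SD at week 6. A skin score with the same underlying severity and its own residual variance of 0.3 ends measurement on crossing a threshold of 3.0, 2.5, 2.0 or 1.5. The model is random-intercept with arm × time and both variance components fixed at 0.4, fitted to all pre-stop data. There were 400 replicates, so Monte Carlo error is about √(2/40)/√400 = 0.011.

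| Stopped, 3-h vs 6-h | Full follow-up | Mixed model, pre-stop data | Week-6 completers only (not a planned analysis) |
|---|---|---|---|
| 1% vs 2% | 0.49 | 0.49 | 0.47 |
| 3% vs 7% | 0.51 | 0.50 | 0.45 |
| 10% vs 19% | 0.51 | 0.48 | 0.40 |
| 27% vs 40% | 0.50 | 0.45 | 0.35 |

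With no true difference the mixed model gave −0.01 to 0.01.

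A second simulation used 12,000 infants per arm, slope SD 0.75, a true effect of 0 or ±0.5 slope SD, TEWL–NSCS correlation 0.3 or 0.7, and a stop at NSCS 5 or more. With 1–58% stopped, the TEWL arm × day effect kept 83–99% of its size with a random intercept and 91–100% with a random slope. With 1–6% stopped it kept 95–99% and 98–100%. NSCS with a random slope moved by at most 0.02 points. Neither simulation includes the planned covariates.

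**6. Unequal trigger, as an illustration only.** In the second simulation, with no true difference and one arm assumed to be stopped at a lower score (13% vs 41% stopped), the random-intercept TEWL estimate moved to about −0.12 or +0.13 SD, the sign depending on which arm was stopped sooner.

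**7. Scale.** At 25 per arm the standard error of a simple mean difference is √(2/25) = 0.28 SD, larger than the mixed-model shifts in steps 5 and 6.

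**The case against.** The strongest reply is that the planned analysis already limits the damage. That stands. A reader might infer that the Aim 2 comparisons rest only on infants whose skin stayed well. They do not: the repeated-measures models use every reading before a stop, and the complete-data phrase in Section 4.b is a recruitment target, not an analysis set. The completer column above is therefore not the plan's estimate.

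A reader might also infer that reaching NSCS 5 ends measurement. Section 8 stops only the intervention. Both simulations assume that measurement ends at the skin trigger, which is the reading least favourable to the plan. If study measurements go on after a Section 8 stop, the loss is confined to infants who lose eligibility under Section 4.d.

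A third inference is that the 6-hour arm will be stopped sooner. No blinding of bedside staff is described, and between changes in that arm "the nurse will peek into the diaper to ensure there are no stool present", so the diapered area is exposed at different intervals. But NSCS is scored twice daily in both arms, and no section makes the trigger depend on arm. Discretionary cream use could differ, but that is conjecture.

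Two technical points also stand. If the stop depends only on a recorded NSCS, a correctly specified likelihood model for NSCS would be unbiased, so part of the NSCS shrinkage reflects rounding and the floor at 3. Part of the random-intercept TEWL shrinkage comes from infants having their own slopes. Neither point covers TEWL or pH, whose models do not contain the skin score, or stops for rash or cream decided outside the score.

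Finally, Section 10 plans descriptive summaries by group and Section 4.d records the criterion met, so a table of stops by arm is feasible from planned data. It is just not named.

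**Conclusion.** The concern holds in a limited form. Section 4.d states a rule under which skin outcomes can stop being measured because of skin condition, and no other section restores them. With few stops and a trigger alike in both arms the result is a modest understatement of any true difference. In the simulations of TEWL-type outcomes, the planned type of model kept about 95% or more when few infants stopped, and 83% or more at stop rates up to 58%. With no true difference it showed essentially no bias.

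A larger bias, in either direction, would need one arm to be stopped sooner. The documents offer no evidence of this and no stop rate, so the actual size is unknown. Section 4.b expects little attrition, but its reason does not address skin-related stops. The point is worth fixing because the loss depends on the outcome, the estimates feed a larger trial, and the remedy is cheap. It does not invalidate the Aim 2 analysis.

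**What to change.** Data collection and analysis only; clinical stopping rules unchanged.

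1. Amend Section 4.d so that stopping the intervention does not stop outcome collection. Continue the EMR outcomes (weight, events, feeding) to week 6 or discharge. Continue NSCS after confirming that it is still charted after a stop. Keep the scheduled TEWL, pH and swab measurements where the care team permits, and flag readings on treated skin.
2. State in Section 10 that all randomized infants are analysed in their assigned arm using all their data.
3. Report skin-related stops by arm, descriptively with a 95% CI, separately from other stops and from discharge. At 25 per arm the half-width for the difference is 1.96 × √(2p(1 − p)/25): 16.6 percentage points at p = 10% and 27.2 at p = 40%. It is too imprecise for a formal test.
4. Reconcile Sections 4.b, 4.d, 4.e.vii and 8 on what is collected after a stop.

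Cost: mostly wording. Table 1 already draws weight, events and feeding from the EMR and follows infections there to two weeks after the study. Post-stop NSCS may need extra collection because Table 1 does not label it EMR. Infants off the intervention would have some extra handling, which Section 8 wants kept low, and readings on treated skin will be less comparable.
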